surface, uneven surfaces) or cognitive demands (e.g. memory, attention, executive function) in a safe environment. The CAREN system is unique from other experimental environments due to the ability to create real-world environments (e.g. street scene with pedestrian and vehicle traffic, trail walking) in which the motor and cognitive aspects of function can be systematically manipulated and measured.

One of the greatest barriers to DT training is the lack of knowledge about effective clinical interventions. The clear benefit to this highly-advanced system is opportunity to investigate mechanisms of dual tasking deficits in a given environment. For example, if participants with PD exhibit increased step variability and decreased stride length during visual memory cognitive tasks that are not seen during verbal memory cognitive tasks, this would provide valuable insight into task selection during a clinical intervention.

**The primary aim of the proposed project is to characterize DT deficits to improve motor, cognitive, and quality of life outcomes in individuals with PD.** A single center study is outlined in Figure 2. Phase 1 of the intervention will involve an in-depth gait analysis on 15 individuals with PD. The purpose of Phase 1 is to generalize characteristics of gait and postural control during specific DT conditions, as in the example provided above. Phase 2 (N=20) involves the clinical translation of these findings. This phase will involve creating a clinical intervention based on the objective information gathered from the CAREN system. Researchers will use the biomechanical data gathered from the CAREN system to prioritize interventions based on given gait and postural control deviations during DT interventions. To continue with the above example, if we find that visual memory tasks lead to decreased stride length, then the therapeutic intervention would be a task such as targeted stepping during gait (e.g. placing stickers slightly wider than normal step length on a treadmill) while performing various visual memory tasks. The intervention will take place 3x/week for a total of 8 weeks. Interventional groups will include: 1) DT clinical group (N=10) and 2) Single task group (N=10). ST training will serve as a control group.

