#### **Aim 2: To create and pilot a DT clinical intervention based on biomechanical analysis from the CAREN system that improves motor and non-motor function of individuals with PD.**

Primary motor outcome will include a 3-D gait analysis using the same parameters as stated in Aim 1. Secondary clinical motor outcome include distance walked during the 2 Minute Walk Test (2MWT) under ST and DT conditions. The Quality of Life in Neurological Disorders (Neuro-QOL) questionnaire will be administered as a quality of life measure. Fall risk will be assessed through the Activities-specific Balance Confidence (ABC) Scale. Cognitive measures, motor, and non-motor tests are described in Table 1.

*Hypothesis:* The DT clinical group will demonstrate the greater improvements in motor and non-motor function compared to the ST groups.

**Research Plan:** A total of 15 individuals diagnosed with idiopathic PD will be included in the initial gait analysis to categorize gait and postural control deficits associated with DT constructs (Figure 2). During Phase 1, all interventions will be carefully documented in order to attribute changes in gait parameters of postural stability with a domain of cognitive function. Phase 2 of the study (N=20) will randomize participants into two groups: 1) DT clinical and 2) ST (Figure 2). *Both groups will receive a time-matched intervention, 3x/week for a total of 8 weeks.* If an individual misses a session, he/she will be required to make it up on a different day of the same week or at the end in order for all 24 sessions to be complete. The entire intervention must be completed within a 10 week period. Intervention sessions for all groups will be completed under the guidance of a physical or occupational therapist who specializes in neurological rehabilitation. Outcome measures for Phase 2 will be administered at baseline, end of treatment (EOT), and EOT+4 weeks (EOT+4) by a blinded evaluator. The purpose of the EOT+4 testing is to gauge the permanence of the training intervention. All participants will be asked to wear a wrist-worn activity monitor that will measure steps/day throughout the duration of Phase 2 participation (baseline through EOT+4).

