**Expected Results:** We anticipate that both DT and ST groups will improve motor and cognitive constructs in ST conditions. It is anticipated that the DT clinical group will improve compared to the ST group in both motor and cognitive performance during DT conditions, quality of life, and fall risk. We do not anticipate that DT constructs will change as a result of ST training due to specificity of training. We anticipate that one of the hallmark findings of this study will be insight to which DT constructs result in specific gait and postural control changes. This will guide clinicians in selecting the most appropriate interventions for individuals with PD, and we anticipate this to be the most important findings of this study to guide future research and clinical decisions.

**Participant Screening:** Participants will be pre-screened by the study coordinator. The following inclusion/exclusion criteria will be used:

Inclusion Criteria:

1. Clinical diagnosis of idiopathic PD
2. Able to provide informed consent
3. Ability to ambulate  $\geq 300$ ft with or without an assistive device
4. Hoehn and Yahr stage 2-4
5.  $\geq 2$  fall related to PD in the past 12 months

Exclusion Criteria:

1. Undergone any surgical procedure for the treatment of PD, such as deep brain stimulation
2. Those who have more than 2 uncontrolled cardiovascular risk factors (uncontrolled heart disease, uncontrolled diabetes, etc.) that would qualify them as a high risk exerciser
3. Musculoskeletal injury or neurological injury other than PD that would restrict physical activity
4. Inability to follow 2 step commands
5. Significant cognitive impairment as designated by  $\geq 3$  errors on the Short Portable Mental Status Questionnaire

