The Effects of Dual Task Training on Motor and Non-Motor Function in Individuals with
Parkinson's Disease

NCT02538029

1.31.19

Statistical Analysis Plan

Phase 1:

Baseline participant demographics and outcome variables will be summarized by group using mean \pm standard deviation for normally distributed variables, median [25th percentile, 75th percentile] for data that is not normally distributed, or N (%) (categorical data). Paired sample t-tests will be used to detect differences in cognitive scores between single and dual-task conditions. A repeated measures analysis of variance (ANOVA) model will be used to determine the effects of the different cognitive dual tasks and single-task on gait performance as measured by the spatial-temporal parameters of gait. When the ANOVA model results in significant differences in comparison from single to dual-task, a post hoc pairwise comparison will be performed to identify which tasks were significantly different from each other. The p-values in multiple comparisons will be adjusted using the Bonferroni correction. All statistical testing will be performed at the 5% level of significance.

Phase 2:

Baseline participant demographics and outcome variables will be summarized by group using mean \pm standard deviation for normally distributed variables, median [25th percentile, 75th percentile] for data that is not normally distributed, or N (%) (categorical data). The intervention effects on outcomes will be assessed using separate linear mixed effects models, each including a random intercept, main effects for group, time, and a group-by-time interaction term. Given a significant group by time interaction, post hoc pairwise comparisons will be performed between groups at each follow-up. In the absence of a group-by-time interaction, the overall change across collapsed groups between each evaluation will be estimated (i.e., change from Baseline to End of Treatment and Baseline to End of Treatment + 4 weeks). All comparisons will be performed at the 0.05 significance level. Within each outcome, pairwise comparisons will be Bonferroni corrected to maintain a 5% type I error rate per outcome.

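### When the group-by-time interaction is not significant, the SAP calls only for a change pooled over both arms and does not require the DT-minus-ST estimate and interval that Aim 2 needs

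*SAP*

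**What the plan says.** The Aim 2 hypothesis in the protocol is a comparison of arms: "The DT clinical group will demonstrate the greater improvements in motor and non-motor function compared to the ST groups". The protocol's Rationale and Impact section gives the ST arm its role: "ST training will serve as a control group". Phase 2 has 10 participants per arm, assessed at baseline, end of treatment (EOT) and four weeks later (EOT+4).

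The Phase 2 section of the SAP fits one random-intercept linear mixed model per outcome, with group, time and their interaction. What follows depends on the interaction test:

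- Significant: "Given a significant group by time interaction, post hoc pairwise comparisons will be performed between groups at each follow-up".
- Not significant: "In the absence of a group-by-time interaction, the overall change across collapsed groups between each evaluation will be estimated", for baseline to EOT and baseline to EOT+4.

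Tests are at 0.05, with Bonferroni correction of pairwise comparisons within each outcome. The Phase 2 section mentions no confidence interval, and the protocol has no analysis section that supplies one.

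**The concern.** The quantity that answers Aim 2 is the difference between arms in change from baseline. In the non-significant branch the SAP requires two things: the p-value of a test on 2 degrees of freedom, which carries no direction, size or precision, and a change averaged over intervention and control. The average cannot show which arm did better.

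The pooled change does have a use. The protocol's Expected Results paragraph says "We anticipate that both DT and ST groups will improve motor and cognitive constructs in ST conditions", and a pooled change bears on that. The same paragraph also says "We do not anticipate that DT constructs will change as a result of ST training due to specificity of training", and a pooled change cannot address that contrast.

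Aim 2 is also framed as a pilot ("To create and pilot a DT clinical intervention based on biomechanical analysis from the CAREN system"). With 10 per arm, a non-significant interaction is weak evidence of no difference, and the size and precision of the DT-minus-ST difference are what a later trial would need. If the difference is shown only after a significant test, the published estimates are also selected for being large.

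**Working it through.** The documents give no effect size, SD, correlation or sample-size calculation, so there is no figure of the plan's own to reproduce. The gap itself is read from the text; the arithmetic shows only how often it would matter.

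**Inputs from the documents:** 10 per arm; 3 visits; random-intercept model; 2-df interaction; alpha 0.05.

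**Assumptions:** two-sided tests; complete data; total outcome variance 1, so effects are in SD of the outcome; correlation between visits rho, so residual variance is 1 − rho; true DT-minus-ST difference in change d at both follow-ups, with no change in the ST arm.

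**1. Chance of reaching the pooled branch.** The interaction F statistic has 2 and (20 − 2) × (3 − 1) = 36 df. The arm-difference profile (0, d, d) has mean 2d/3 and centred sum of squares (4/9 + 1/9 + 1/9)d² = (2/3)d². The noncentrality is therefore

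lambda = (10/2) × (2/3)d² / (1 − rho).

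For d = 0.8 and rho = 0.5, lambda = 5 × 0.667 × 0.64 / 0.5 = 4.27. The power is 0.41, so the pooled branch is reached with probability 0.59. For all settings, P(interaction not significant) is:

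| d (SD) | rho 0.5 | 0.6 | 0.7 | 0.8 | 0.9 |
|---|---|---|---|---|---|
| 0.5 | 0.82 | 0.78 | 0.72 | 0.60 | 0.30 |
| 0.8 | 0.59 | 0.50 | 0.38 | 0.19 | 0.02 |
| 1.0 | 0.41 | 0.30 | 0.18 | 0.05 | 0.001 |

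If half the effect is lost by EOT+4, the profile (0, d, d/2) has centred sum of squares d²/2 and the branch is reached more often:

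| d (SD) | rho 0.5 | 0.6 | 0.7 | 0.8 | 0.9 |
|---|---|---|---|---|---|
| 0.5 | 0.85 | 0.83 | 0.78 | 0.69 | 0.44 |
| 0.8 | 0.68 | 0.61 | 0.50 | 0.32 | 0.06 |
| 1.0 | 0.53 | 0.44 | 0.30 | 0.13 | 0.006 |

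**2. Chance of reaching that branch with a significant pooled change.** This was simulated with 100,000 trials per setting, a sustained effect, and two pooled changes each tested at 0.025 on 36 df:

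| d (SD) | rho 0.5 | 0.6 | 0.7 | 0.8 | 0.9 |
|---|---|---|---|---|---|
| 0.5 | 0.16 | 0.18 | 0.21 | 0.25 | 0.21 |
| 0.8 | 0.25 | 0.25 | 0.24 | 0.15 | 0.02 |
| 1.0 | 0.24 | 0.21 | 0.14 | 0.05 | 0.001 |

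The true pooled change here is (d + 0)/2, half the DT effect. These are not false positives, but they carry no information on DT versus ST.

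**3. Selection when the difference is shown only after significance.** For a true d of 0.8 and rho from 0.5 to 0.8, the observed DT-minus-ST difference at EOT averages 1.13 down to 0.88 SD in trials with a significant interaction, and 0.57 down to 0.48 SD in the others. In the others the pooled change averages 0.40 SD.

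**4. Precision of the missing estimate.** The variance of the DT-minus-ST difference in change is 2 × 2(1 − rho)/10 = 4(1 − rho)/10. The half-width is t(36) × sqrt(4(1 − rho)/10), with t = 2.028 (95%) or 2.339 (97.5%, Bonferroni for two contrasts). At rho = 0.5 this is 2.028 × 0.447 = 0.91 SD.

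| Half-width (SD) | rho 0.5 | 0.6 | 0.7 | 0.8 | 0.9 |
|---|---|---|---|---|---|
| 95% | 0.91 | 0.81 | 0.70 | 0.57 | 0.41 |
| 97.5% | 1.05 | 0.94 | 0.81 | 0.66 | 0.47 |

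**The case against.** **Aim 2 is tested in every case.** The interaction is the between-arm test of change, and post hoc comparisons after a significant interaction are a conventional sequence. The SAP nowhere presents the pooled change as evidence of a DT benefit. This stands: there is no wrong test and no inflated error rate. A p-value is still not an estimate.

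**The SAP does not forbid reporting the coefficients.** They are in the fitted model, and nothing bars giving them with intervals. This also stands, so the claim is limited to what the SAP requires. It does, however, name a specific output for this branch, and that output is a different one.

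**Arm summaries may already show direction and size.** The SAP says "Baseline participant demographics and outcome variables will be summarized by group". If the first word does not govern the outcome variables, means by arm at every visit would be given. The baseline-only reading is the more natural one, and neither reading supplies a contrast or its interval.

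**The significant branch is thin too.** It compares arms at each follow-up, does not specify differences in change, and mentions no interval. That is correct, and the remedy should cover both branches.

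**The size rests on assumptions.** The branch probabilities run from over 80% to under 1%. The joint probabilities in step 2, and the statement that the pooled change is half the DT effect, need an ST arm that does not change. The protocol expects that only for DT constructs, so those figures should not be carried over to outcomes measured in ST conditions. The branch probabilities in step 1 depend only on the difference between arms and are unaffected.

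**Conclusion.** The concern holds. Followed as written, the SAP requires no DT-minus-ST estimate or interval for any Phase 2 outcome whose interaction is not significant, although Aim 2 is a comparative hypothesis. The gap is in the specified output, not in the model or the test.

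Under the assumptions stated, the pooled branch is common for moderate effects and rare only when effect and correlation are both high. For a sustained 0.5 SD benefit it is the more likely branch at every correlation from 0.5 to 0.8. Those frequencies depend on inputs the documents do not give; the gap in the SAP text does not. It should be fixed, and confidence in the finding is high.

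**What to change.** Add one or two sentences to the Phase 2 section of the SAP:

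- For every outcome, report the DT-minus-ST difference in change from baseline at EOT and at EOT+4, with confidence intervals, from the mixed model already specified and whatever the interaction p-value, with Bonferroni adjustment for the two contrasts.
- Keep the pooled change as a secondary, uncontrolled result that bears on the expectation of improvement in both arms under ST conditions, and state that it is not evidence of a DT benefit.

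This covers both branches and removes the selection described above. It needs no new data, model, sample size or alpha. The price is that some intervals will be wide: after Bonferroni, about 1.05 SD either side at a correlation of 0.5 and 0.66 SD at 0.8. Such intervals will often include both no effect and a large one. They will seldom settle Aim 2, but they show what a pilot of this size can say.
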